APPENDIX A. DRUG DIARY

CONA Study Participant Self-Administration Study Drug Diary

OTHER MEDICATIONS TAKEN

If you take a daily medication (prescribed or otherwise), please use one line per drug and indicate the start and stop dates under the "Date(s) Taken" section (i.e. 6/2/15-6/5/15).

Participant ID:				Drug Name	Dose	Dates Taken	Reason Taken
Protocol #:	15-17919	_					
Your MD:	[name]	[contact]				
Your RN:	[name]	[contact]				
Your CRC:	[name]	-	[contact]				
rour exe.	[name]	- I none.	[contact]				
STUDY DRUG	GINSTRUCTIONS	S:					
How Much:	Your dose is 5mL.						
How Often:	You will take one	dose three	times per day.				
When:	You should take a dose every 6-8 hours.						
	rou should take a	dose ever	y 6-6 nours.				

SPECIAL INSTRUCTIONS:

Store vials in your refrigerator. Use an entire vial at once; do not store any remaining medication. Remember to take two puffs of albuterol 15 minutes before taking your study medication.

If you forget to take one or more doses, and it is almost time for the next dose, skip the missed dose and take the next dose when it is due. Do not take a double dose to make up for the dose that you missed.

Please bring any unused study drug, all empty vials, and this diary to the next clinic visit.

Participant Initials:	Date:	
-----------------------	-------	--

FOR STUDY TEAM USE ONLY						
Staff Initials:	Date Dispensed:	Date Re	eturned:			
# Vials Dispensed:		#Vials Returned:				
# Vials that should have b	een taken:					
Discrepancy Notes:						

Page 1 of 2

DOSING AND SYMPTOM LOG

Please indicate the date and time each dose of study medication is taken. Please record any asthma-related side effects in the appropriate column. Other symptoms can be recorded in the "Other" column. Please evaluate the severity of the symptom according to the following scale:

None (0): No symptom noted

Mild (1): Awareness of symptom; easily tolerated and did not affect ability to perform normal daily activities. Symptom did not require treatment.

Moderate (2): Significant discomfort which interfered with ability to perform normal daily activities. Symptom was easily resolved with at home medication or simple therapeutic intervention.

[figure not shown]
Severe (3): Marked discomfort with an inability to carry out normal daily activities. Symptom required new medication and/or therapeutic intervention in order to resolve.

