2.1 Risk / Benefit Assessment

Inhaled NAC carries a relatively low risk profile. The main side effects from inhalational use are nausea, reported in 2-7% of cases, and vomiting, reported in 9-12% of cases. Other reported side effects without documented incidence rates include stomatitis, cough, hemoptysis, rhinorrhea, fever, and chills. Rarely, NAC has been associated with increased intracranial pressure and somnolence. Although these later side effects have been documented in the medical literature, our team of physicians, experienced in using NAC clinically, has not encountered these more serious side effects.

Mucus impaction and the concomitant airway obstruction are associated with severe activity limitation and disease-associated impairment. Currently, there are few effective

mucolytics utilized as part of standard clinical care of patients with severe asthma. This is due in part to the lack of clinical trial data on the effectiveness of NAC, the only nebulized mucolytic currently indicated for asthma. Our preliminary data, utilizing CT imaging and a novel scoring system, can identify and target a subgroup of patients who may benefit from inhaled mucolytic treatment more so than the asthmatic population as a whole.

To minimize risk, our study team of experienced clinicians will supervise the initial administrations of the study drug in a controlled environment located within a hospital setting.

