5.2 Secondary Efficacy Endpoints

We intend to examine the effect of the treatment on CT mucus score in a subset of participants. Because the CT mucus score is a novel measurement, we do not have preliminary data to describe the natural history of mucus in the airway over time or with treatment. Therefore, for the purpose of this study, we intend to describe any changes we observe.

With respect to drug tolerability, we will first analyze the two treatment periods to assess any negligible carryover effects and then describe frequencies of reported side effects.

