5.3 Safety Evaluations

All participants will have their first dose of treatment or normal saline administered in the clinical laboratory environment under the supervision of a study nurse or study clinician. Participants will receive instruction on nebulizer use utilizing a teach-back method to ensure comprehension. Participants who are unable to successfully teach back nebulizer setup or drug self-administration will be excluded from continued participation.

Additionally, while acute anaphylactoid reactions have only been observed in the setting of IV administered NAC, each participant will be observed for 30 minutes following initiation of each new study period by a study nurse or study clinician.

All participants will be asked to complete a log of study drug administration, concomitant medications, and any subjective side effects (appendix A). Additionally, participants will have access via pager to a study nurse or clinician 24 hours a day, 7 days a week.

Interim safety evaluations will be triggered if anticipated adverse events exceed frequencies documented in the literature, unanticipated adverse events occur, or rare but serious adverse events occur. Definitions of these terms and details of our safety evaluation plan are described in section 14.

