8.1.15 Adverse Events

Information regarding occurrence of adverse events will be captured throughout the study. Duration (start and stop dates and times), severity/grade, outcome, treatment and relation to study drug will be recorded on the case report form (CRF).

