10 ADVERSE EXPERIENCE REPORTING AND DOCUMENTATION

10.1 Adverse Events

An adverse event (AE) is any untoward medical occurrence in a clinical investigation of a patient administered a pharmaceutical product and that does not necessarily have a causal relationship with the treatment. An AE is therefore any unfavorable and unintended sign (including an abnormal laboratory finding), symptom or disease temporally associated with the administration of an investigational product, whether or not related to that investigational product. An unexpected AE is one of a type not identified in nature, severity, or frequency in the current Investigator's Brochure or of greater severity or frequency than expected based on the information in the Investigator's Brochure.

The Investigator will probe, via discussion with the participant, for the occurrence of AEs during each participant visit and record the information in the site's source documents. Adverse events will be recorded in the participant CRF. Adverse events will be described

Version #:1.5 Version Date: 8/5/2016 Page 29 of 41

by duration (start and stop dates and times), severity, outcome, treatment and relation to study drug, or if unrelated, the cause.

AE Severity

The National Cancer Institute's Common Terminology Criteria for Adverse Events (CTCAE) Version 3.0 should be used to assess and grade AE severity, including laboratory abnormalities judged to be clinically significant. The modified criteria can be found in the study manual. If the experience is not covered in the modified criteria, the guidelines shown in Table below should be used to grade severity. It should be pointed out that the term "severe" is a measure of intensity and that a severe AE is not necessarily serious.

Table 3. AE Severity Grading

Severity (Toxicity Grade)	Description
Mild (1)	Transient or mild discomfort; no limitation in activity; no medical intervention or therapy required. The participant may be aware of the sign or symptom but tolerates it reasonably well.
Moderate (2)	Mild to moderate limitation in activity, no or minimal medical intervention/therapy required.
Severe (3)	Marked limitation in activity, medical intervention/therapy required, hospitalizations possible.
Life-threatening (4)	The participant is at risk of death due to the adverse experience as it occurred. This does not refer to an experience that hypothetically might have caused death if it were more severe.

AE Relationship to Study Drug

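### The drug diary prompts for four respiratory symptoms at every dose but leaves nausea and vomiting, the main inhaled-NAC effects named in section 2.1, to a free 'Other' box, so their frequencies are at risk of under-recording

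*Combined protocol and SAP*

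**What the plan says.** Section 2.1 ranks the known effects of the inhaled drug: "The main side effects from inhalational use are nausea, reported in 2-7% of cases, and vomiting, reported in 9-12% of cases". It then adds effects for which it has no rates: "Other reported side effects without documented incidence rates include stomatitis, cough, hemoptysis, rhinorrhea, fever, and chills".

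Section 5.3 gives the diary a wide scope: "All participants will be asked to complete a log of study drug administration, concomitant medications, and any subjective side effects (appendix A"). Section 7.7 likewise has participants note adverse events in it. The form itself is narrower. It has one row per dose, three doses a day for seven days. Each row has named columns for wheeze, cough, chest tightness and shortness of breath, plus one free-text column. The instruction reads "Please record any asthma-related side effects in the appropriate column. Other symptoms can be recorded in the" 'Other' column. Its worked example shows a graded runny nose in that column.

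The diary is not the only route. Section 10.1 states: "The Investigator will probe, via discussion with the participant, for the occurrence of AEs during each participant visit". Section 8.1.15 states: "Information regarding occurrence of adverse events will be captured throughout the study".

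The frequencies are used in three places. For tolerability, section 5.2 will "describe frequencies of reported side effects". Section 14.4 tabulates adverse events by treatment group, including the number of patients affected. Section 5.3 sets a safety trigger: "Interim safety evaluations will be triggered if anticipated adverse events exceed frequencies documented in the literature".

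**The concern.** The form and its purpose do not match well. Respiratory symptoms are asked about 21 times in each treatment period. A 0 in one of those columns records that the symptom was absent. Nausea and vomiting reach the diary only if the participant thinks to write them in, and an empty 'Other' cell may mean either no symptom or no entry.

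These are also the only two NAC effects for which section 2.1 gives a numerical rate, so they are the only ones for which the section 5.3 comparison with the literature has a stated benchmark. With 30 participants the expected counts are very small, and one or two missed cases could change both the tolerability description and the result of that comparison.

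**Working it through.** The plan states no capture rate for side effects, so there is no figure of its own to reproduce. The check sets the recording routes side by side and then shows the possible scale.

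**1. What each route asks about nausea and vomiting**

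| Route | Where | Prompt for nausea or vomiting? |
|---|---|---|
| Diary, per dose | Appendix A | No named column; permissive 'Other' |
| Investigator questioning at each visit | 10.1 | Open discussion; no checklist |
| CRF capture throughout | 8.1.15 | Lists fields to record; no prompt |
| Steps at Visits 5 and 8, the ends of the two treatment periods | 9.5, 9.8 | AE recording 'and/or' diary review |
| Steps at Visits 6 and 7 | 9.6, 9.7 | No AE step listed |
| Supervised first dose and 30-minute observation | 5.3 | Covers only the start of each period |

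The general rule in 10.1 requires questioning at every visit, but the visit lists do not carry it through. At Visits 5 and 8 the 'and/or' can be satisfied by reading a diary that did not ask. Section 14 does not say how diary and CRF entries are reconciled, or which source feeds the section 5.3 trigger.

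**2. Scale, by assumption**

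Inputs:
- n = 30 participants exposed to NAC (14.6, crossover, assuming all receive it).
- p = 0.02 and 0.07 for nausea, 0.09 and 0.12 for vomiting (2.1), read as proportions of participants.
- c = the proportion of affected participants recorded by any route. The documents give no value. The values 1, 0.75 and 0.5 are assumed to show a range.

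Formulas: expected recorded cases = 30 × p × c; chance of recording none = (1 − p × c)^30.

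| Effect, p | Expected cases at c = 1 / 0.75 / 0.5 | Chance of none at c = 1 / 0.75 / 0.5 |
|---|---|---|
| Nausea 0.02 | 0.60 / 0.45 / 0.30 | 54.5% / 63.5% / 74.0% |
| Nausea 0.07 | 2.10 / 1.58 / 1.05 | 11.3% / 19.8% / 34.3% |
| Vomiting 0.09 | 2.70 / 2.03 / 1.35 | 5.9% / 12.3% / 25.1% |
| Vomiting 0.12 | 3.60 / 2.70 / 1.80 | 2.2% / 5.9% / 15.6% |

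For example, with vomiting at 0.12 and c = 0.5: (1 − 0.06)^30 = 0.94^30 = 0.156.

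**3. Effect on the section 5.3 comparison**

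To exceed the upper literature rate in 30 participants, nausea needs at least 3 cases (30 × 0.07 = 2.1) and vomiting at least 4 (30 × 0.12 = 3.6). Suppose the true rates were double those upper values, 0.14 and 0.24 (a further assumption). With X binomial(30, true rate × c):

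| | c = 1 | c = 0.75 | c = 0.5 |
|---|---|---|---|
| Nausea, P(X ≥ 3) | 81% | 62% | 35% |
| Vomiting, P(X ≥ 4) | 95% | 81% | 49% |

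Incomplete capture, if it occurred, would weaken the trigger. The tables do not show that it will occur.

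**The case against.** A reader might infer that nausea and vomiting will certainly be under-counted, or that the trial never asks about them. The documents do not support either reading. Section 10.1 has the investigator ask about adverse events at each visit, 8.1.15 captures them throughout, and the 14.4 tabulation is not limited to diary entries. The diary's own example teaches participants to grade a non-respiratory symptom under 'Other', and staff can be paged at any hour (5.3). Nor is a per-dose prompt strictly needed: 14.4 counts patients with the event, and a yes/no answer about the past week would supply that count.

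A reader might also infer a bias between NAC and saline. That does not follow, because the same form is used in both periods.

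It can also be said that the prompted columns do bear on NAC tolerability. Cough is a listed effect in 2.1, and 7.4.1 cites lung irritation as the reason for albuterol before each dose. Finally, section 2.1 does not say whether its rates came from prompted or volunteered reports. If they were volunteered, an unprompted count is the like-for-like comparison, and added columns could set off the trigger too readily.

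Most of this stands, and it limits the point to a risk. It does not remove the point. The visit questioning has no nausea or vomiting item, the steps at Visits 5 and 8 allow it to be replaced by diary review, and a blank 'Other' cell remains ambiguous. An identical form in both periods does not protect an absolute frequency, or a comparison with an external rate.

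**Conclusion.** The point holds as a risk of unknown size. The two effects that the protocol ranks first are collected less systematically than four respiratory symptoms, and the back-up routes only partly make up for it. The 75% and 50% capture rates, and the doubled true rates, are assumptions that show how much small counts could move. They do not estimate a loss. This is an opportunity for a cheap improvement in data collection, not an error in the plan, and it does not affect the FEV1 analysis.

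**What to change.** Add 'Nausea' and 'Vomiting' columns to the Appendix A dosing and symptom log, with the same 0-3 rating, and use the form in both treatment periods. In 14.4, tabulate prompted symptoms by treatment, with NAC and saline side by side, separately from volunteered 'Other' entries.

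The cost is a one-page form revision. As the diary is a protocol appendix, it would go through IRB approval under 16.1. No visit or treatment changes.

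The downside is that prompting raises reported rates in both arms. Prompted rates should therefore be read against the saline period. They should be compared with the literature rates in the 5.3 trigger only with caution, because the documents do not say how those rates were collected.
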